3.1.8 Laboratory Values Above or Below Limits of Quantification

For laboratory values less than the lower limit of quantification (LLQ), half of the lower limit value (i.e. LLQ/2) will be used in the analysis. For values greater than the upper limit of quantification (ULQ), the upper limit value (i.e., ULQ) will be used in the analysis.

3.2 Analysis Populations

3.2.1 Intent-to-Treat (ITT) Population

The ITT Population will include all participants who are randomized into the study. Treatment classification will be based on the randomized treatment.

3.2.2 The Full Analysis Set (FAS)

The FAS will include all participants who are randomized into the study, take any study drug, and have at least 1 post-treatment lipid data assessment. Treatment classification will be based on the randomized treatment.

3.2.3 Modified Intent-to-Treat (mITT) Population

The mITT Population will include all randomized participants who receive at least 1 dose of any study drug and have data for both the Day 1 and Day 84 LDL-C assessments. Treatment classification will be based on the randomized treatment.

3.2.4 The mITT On-Treatment Population

The mITT On-Treatment Population will include all randomized participants who receive at least 1 dose of any study drug, have data for both the Day 1 and Day 84 LDL-C assessments, are in the placebo or ezetimibe only arm or, if in the fixed dose combo or obicetrapib only arms have an obicetrapib plasma concentration at Visit 4 (Day 84) that was >100 ng/mL. Treatment classification will be based on the randomized treatment.

Rationale: <100 ng/mL is more than three standard deviations from the mean obicetrapib concentration observed in both the ROSE (protocol number TA-8995-201) and TULIP (protocol number TA-8995-03) studies (with a very similar participant population compared to TANDEM (protocol number OBEZ-301) at respectively Week 4 and Week 12 [1-3]. In addition, in none of the previous conducted studies (3 clinical studies and 2 Phase 1) PK / PD studies the minimal observed obicetrapib concentration for Cmax was below 100 μg/mL.

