7.2 Pharmacokinetic Assessments

Plasma obicetrapib and ezetimibe concentrations, both in combination and each as monotherapy, will be assessed at the scheduled PK collection times.

A PK sample will be collected prior to study drug administration for trough measurements of obicetrapib and ezetimibe in plasma. At Visit 2 (Day 1), Visit 3 (Day 28), Visit 4 (Day 84), and the EOT Visit, in cases of early discontinuation of study drug or study, participants should take study drug after a trough PK sample has been collected.

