9 STATISTICS

9.1 Analysis Populations

The Intent-to-Treat (ITT) Population will include all participants randomized into the study. Treatment classification will be based on the randomized treatment.

The Full Analysis Set (FAS) will include all participants who are randomized into the study, take any study drug, and have at least 1 post-treatment lipid data assessment. Treatment classification will be based on the randomized treatment.

The Modified ITT (mITT) Population will include all randomized participants who receive at least 1 dose of any study drug and have data for both the Day 1 and Day 84 LDL-C assessments. Treatment classification will be based on the randomized treatment.

The mITT On-Treatment Population will include all randomized participants who receive at least 1 dose of any study drug, have data for both the Day 1 and Day 84 LDL-C assessments, and have an obicetrapib plasma concentration at Visit 4 (Day 84) that was >100 ng/mL. Treatment classification will be based on the randomized treatment.

The Per-Protocol (PP) Population will include all participants in the mITT Population who did not experience a major protocol deviation that potentially impacted the primary efficacy endpoint. The PP Population, along with the reason for exclusion, will be finalized prior to study unblinding.

The Safety Population will include all participants who receive at least 1 dose of any study drug. Treatment classification will be based on the actual treatment received. The Safety Population will be the primary population used for the safety analyses.

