3.4 Efficacy Assessment

The ITT Population will be the primary population for the efficacy analysis. Efficacy will also be analyzed using the FAS, the mITT Population, mITT On-Treatment Population, and PP Population as supportive analyses. Primary and secondary efficacy endpoints will be presented in listings.

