Supplemental analyses will be performed for the primary efficacy endpoint in order to assess any differences with the results from the primary analysis and investigate what effect, if any, protocol violations have on the trial results. In the first supplemental analysis, a mixed model for repeated measures (MMRM) approach will be utilized. The analysis will include fixed effects for treatment group, visit, and treatment-by-visit interaction, along with covariates of the Baseline LDL-C value as a continuous covariate. The restricted maximum likelihood estimation approach will be used with an unstructured covariance matrix. The LS mean, standard errors, and 2-sided 95% confidence intervals for the treatment group and for the comparison of the treatment groups (FDC treatment vs. placebo, FDC treatment vs. ezetimibe 10 mg, and FDC treatment vs. obicetrapib 10 mg, and obicetrapib 10 mg vs. placebo) will be provided. The MMRM approach will include all available assessments of percent change in LDLC from Day 1, Day 28, and Day 84. The model assumes that the data are missing at random (MAR). If any data are missing, the model will use all information from the other time points to estimate the mean treatment difference at the given time point. No imputation of missing data will be performed. The analysis will be conducted for ITT Population.

Additional supplementary analysis will be performed using the ANCOVA model from the primary analysis based on the FAS, mITT, mITT On-Treatment, and PP populations. No imputation for missing data will be performed for the analysis.

Secondary Estimand

A secondary estimand will be assessed for the primary efficacy endpoint. The secondary estimand is defined by the following key attributes:

- Treatment:

- obicetrapib 10 mg + ezetimibe 10 mg FDC treatment versus placebo,
 ezetimibe 10 mg monotherapy, and obicetrapib 10 mg monotherapy, and obicetrapib 10 mg monotherapy versus placebo
- Target Population: participants who are randomized into the study
- Analysis Population: The ITT Population
- **Intercurrent events**: treatment discontinuation, prohibited medication use
- Analysis set and handling of intercurrent events: A hypothetical strategy will be used. All available values of LDL-C at Baseline and Day 84 will be included in the calculation of the percentage change from Baseline to Day 84.

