- **Population level summary**: The difference in LS mean percentage change in LDL-C from Baseline to Day 84 between obicetrapib 10 mg + ezetimibe 10 mg FDC treatment versus placebo, ezetimibe 10 mg monotherapy, and obicetrapib 10 mg monotherapy, and obicetrapic 10 mg monotherapy versus placebo.

This hypothetical estimand represents the treatment effect of FDC treatment relative to placebo, ezetimibe 10 mg monotherapy, and obicetrapib 10 mg monotherapy, and the treatment effect of obicetrapib 10 mg monotherapy relative to placebo at Day 84 in the randomized participants had they remained on their randomized treatment for the entire planned treatment period. This estimand uses a hypothetical strategy to handle intercurrent events and is intended to provide an estimation of the achievable study treatment effect if participants take the treatment as planned. The resulting missing values (corresponding to unobserved values or excluded values following study drug discontinuation or the use of prohibited medication) will be implicitly handled by using a MMRM approach under the assumption of missing at random. The model will be similar to the MMRM approach described previously for the supplemental analysis of the primary efficacy endpoint. The supplementary analysis for the primary efficacy endpoint assessed by secondary estimand will be performed using the mITT On-Treatment populations.

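### The mITT On-Treatment Population checks drug exposure in only two of the four arms, which tilts its supportive FDC-versus-ezetimibe contrast toward FDC

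*SAP*

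**What the plan says.** SAP 3.2.4 requires at least one dose and LDL-C at Day 1 and Day 84. It then admits participants who "are in the placebo or ezetimibe only arm or, if in the fixed dose combo or obicetrapib only arms" have plasma obicetrapib above 100 ng/mL at Visit 4. The rationale in that section defends the threshold. It does not discuss applying an exposure test in two arms only.

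Protocol 9.1 has the same threshold without any arm restriction: members must "have an obicetrapib plasma concentration at Visit 4 (Day 84) that was >100 ng/mL". Read literally, that would empty the placebo and ezetimibe arms. SAP section 5 lists only the subgroup analysis as a change from the protocol.

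The set has two uses:

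- SAP 3.4: "Efficacy will also be analyzed using the FAS, the mITT Population, mITT On-Treatment Population, and PP Population as supportive analyses". For the primary endpoint, SAP 3.4.1 adds: "Additional supplementary analysis will be performed using the ANCOVA model from the primary analysis based on the FAS, mITT, mITT On-Treatment, and PP populations". This is done without imputation, and the text does not remove values obtained after study drug was stopped.
- The hypothetical (secondary) estimand, SAP 3.4.1: "The supplementary analysis for the primary efficacy endpoint assessed by secondary estimand will be performed using the mITT On-Treatment populations".

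Adherence data exist in every arm. Protocol 5.5.4 provides pill counts for all participants, each of whom takes two tablets and one capsule. Protocol 7.2 provides drug levels: "A PK sample will be collected prior to study drug administration for trough measurements of obicetrapib and ezetimibe in plasma". Protocol 4.5 asks participants who stop study drug to return for Visit 4.

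**The concern.** Take two participants who both stop study drug before Day 28 and both return at Day 84. The one randomized to FDC leaves the set if the obicetrapib level is not above 100 ng/mL. The one randomized to ezetimibe stays and counts as on treatment. The FDC mean then describes people with confirmed exposure, while the ezetimibe mean is diluted by people who took nothing.

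FDC-versus-ezetimibe is one of the four co-primary contrasts and the one that shows what obicetrapib adds to ezetimibe. A supportive estimate described as on-treatment should not lean toward one side of it. The hypothetical estimand asks about the effect with treatment taken as planned, and checking exposure in half the arms does not address that evenly.

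There is also a practical difficulty. SAP 4.2 has exclusions from analysis populations settled before unblinding, but membership under 3.2.4 cannot be decided without knowing the arm.

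**Working it through.** **Planning figures (Protocol 9.2.4, SAP 2.2.2).** With 95 evaluable per arm, SD 25 and one-sided alpha 0.025, the normal approximation gives power above 99.9% for 30 points, 99.98% for 20, 98.5% for 15 and 91.1% for 12 (90.8% by the noncentral t). Enrollment is 380 / 0.95 = 400. The stated figures reproduce. The documents give no figure for the On-Treatment set.

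**Inputs**

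- E, the ezetimibe effect on LDL-C: 10 points, implied by the planning differences (FDC-placebo 30 minus FDC-ezetimibe 20); or 15.1 (added to a statin) or 18.58 (monotherapy), both cited in Protocol 1.5.1.
- q, the share taking no drug: assumed, 3% to 10%. The documents give no value.
- g, the points by which non-takers do worse for reasons other than study drug: assumed, 0 to 5.
- Non-takers are assumed to lose the whole drug effect.

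**FDC versus ezetimibe.** Let the difference among takers be 20, so FDC lowers LDL-C by A = 20 + E.

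- Filter in both arms: A − E = 20.
- SAP filter (FDC only): A − [(1 − q)E − qg] = 20 + q(E + g).
- Excess over the even filter: q(E + g).

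With g = 0:

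| E | q = 3% | q = 10% |
|---|---|---|
| 10 | 0.30 | 1.00 |
| 15.1 | 0.45 | 1.51 |
| 18.58 | 0.56 | 1.86 |

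Widening to q = 2% to 10% and g = 0 to 5 gives 0.02 × 10 = 0.2 up to 0.10 × 23.58 = 2.4 points. The sign is the same throughout. At q = 5% the range is 0.5 to 1.2.

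Against the unfiltered mITT contrast, (1 − q) × 20, the difference is q(A + g), or 0.6 to 4.4 points over the same wider range. Most of that comes from removing FDC non-takers, which an on-treatment set is meant to do.

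**FDC and obicetrapib versus placebo.** A placebo non-taker loses no drug effect, so the excess over an even filter is qg. It is 0 if g = 0, and 0.1 to 0.5 points if g = 5 and q = 2% to 10%. Simulating 20,000 null trials with 95 per arm gave favourable one-sided rejection rates of 0.024 (q = 5%) and 0.027 (q = 10%) with g = 0, and 0.029 and 0.038 with g = 5. The nominal rate is 0.025.

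**FDC versus obicetrapib.** The filter is the same in both arms, so this asymmetry does not arise.

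**Would a raw 80% to 120% pill-count rule serve?** SAP 3.3.7 counts an unreturned kit as fully used, and Protocol 5.5.2 puts 36 days' supply in each 28-day kit. Over 84 days:

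- Fully adherent, returns no kit: 3 × 36 = 108; 108 / 84 = 129%, excluded.
- Takes the first kit correctly and returns it, then takes nothing and returns neither later kit: 28 + 72 = 100; 100 / 84 = 119%, kept.

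That rule would misclassify in both directions.

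**The case against.** The strongest reply is that little depends on this set. ITT under a treatment policy strategy is primary, and ITT is also the stated analysis population of the hypothetical estimand. In the model described for that estimand, values after discontinuation or prohibited medication are excluded in every arm, so only unrecorded non-adherence remains uneven there. The threshold is described as more than three SDs below typical levels, so the filter removes near non-takers and q may be small. The largest main-range excess, 1.86 points, is about half the planned standard error (25 × √(2/95) = 3.6). Population counts by arm (SAP 3.3.3), baseline tables (3.3.4) and compliance tables (3.3.7) give some transparency, and the mITT and PP sets have arm-neutral definitions. All of this stands and limits the point. It does not remove the tilt, and SAP 3.3.3 promises exclusion reasons for the PP Population only.

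A reader might infer two stronger things. The first is that the placebo contrasts are biased as well. Against an even on-treatment comparison that requires non-adherence to be prognostic in itself, for instance through skipped background therapy. This is plausible, but nothing in the documents shows it. The second is that the trial's conclusion or type I error is at risk. No confirmatory test uses this set.

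It is also tempting to require both an obicetrapib and an ezetimibe level. FDC would then face two drug-level tests and each monotherapy arm one, so FDC-versus-obicetrapib, now filtered equally, would become uneven. The documents give no ezetimibe threshold to support such a test.

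**Conclusion.** The exposure filter is one-sided on the face of SAP 3.2.4, and in this supportive population it moves FDC-versus-ezetimibe toward FDC whenever ezetimibe works and some ezetimibe participants do not take it. The size is roughly 0.3 to 1.9 points against a planned 20. It rests on an assumed 3% to 10% share taking no drug, complete loss of effect in them, and an ezetimibe effect of 10 to 18.58 points. With the effect implied by the plan's own differences, the range is 0.3 to 1.0. For FDC-versus-placebo and obicetrapib-versus-placebo, bias is possible but conditional. FDC-versus-obicetrapib and all confirmatory tests are unaffected. This is a modest defect in a supportive analysis and cheap to correct before unblinding.

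**What to change.** Redefine the set with a criterion that is identical in all four arms and can be applied before unblinding:

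- no recorded permanent discontinuation of study drug before Day 84; and
- pill-count compliance of at least 80%, with unreturned kits treated as unknown instead of fully used, and one stated rule for unknown counts in every arm.

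Keep obicetrapib above 100 ng/mL as an additional restriction whose results are reported separately. Use an ezetimibe-level criterion only as a sensitivity analysis, and only if a threshold can be justified. Report exclusions by arm and reason, and label the result a non-randomized comparison. Align Protocol 9.1 with the SAP definition and list the change in SAP section 5.

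The cost is SAP and protocol wording, some programming for the kit rule, and a slightly smaller supportive population. No new samples or visits are needed. The set would still be selected after randomization, which is why the label matters.

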3.2.5 Per-Protocol (PP) Population

The PP Population will include all participants in the mITT Population who did not experience a major protocol deviation that potentially impacted the primary efficacy endpoint. The PP Population, along with the reason for exclusion, will be finalized prior to study unblinding.

3.2.6 Safety Population

The Safety Population will include all participants who receive at least 1 dose of any study drug. Treatment classification will be based on the actual treatment received. The Safety Population will be the primary population used for the safety analyses.

3.3 Subject Data and Study Conduct

3.3.1 Subject Disposition

Counts and percentages of subjects who were randomized, completed the treatment period, discontinued treatment (including primary reason for discontinuation), completed the study, and prematurely discontinued from the study (including primary reason for discontinuation) will be summarized by treatment group and overall.

For each scheduled visit, counts and percentages of subjects who did not complete the visit, completed in-clinic, completed in-clinic and remote, or completed will be summarized by treatment group and overall. The denominator for calculating percentages will be based on the number of randomized participants.

3.3.2 Protocol Deviations

Protocol deviations will be identified based on clinical data as defined in the Protocol Deviation Plan, where all protocol deviations will be defined as either CSR reportable or non-CSR reportable deviations. The CSR reportable protocol deviations will be categorized and separated by treatment group. The CSR reportable deviations will include all randomized subjects using counts and percentages.

3.3.3 Analysis Populations

Counts and percentages of subjects in each analysis population will be summarized by treatment group and in total based on all randomized subjects. Reasons for exclusion from PP Population will also be summarized.

3.3.4 Demographic and Baseline Characteristics

The following demographic and baseline characteristics will be summarized with descriptive statistics or counts and percentages of subjects as appropriate by treatment group and overall, for the ITT Population:

- Age and age categories (<65 years, 65 to 74 years, and 75+ years)
- Sex
- Race
- Ethnicity
- Height
- Weight
- Body Mass Index (BMI)
- HIS, non-HIS. HIS include atorvastatin 40 or 80 mg, rosuvastatin 20 or 40 mg. Participants will be defined as having HIS therapy based on the data collected in the eCRF and if any following were used at baseline: average daily dose of atorvastatin ≥40 mg or average daily dose of rosuvastatin of ≥20 mg. Participants having any other doses of statin or another statin or no statin will be defined as having non-HIS therapy.
- The history of ASCVD (Yes, No).

If they differ from the ITT Population, summaries will also be provided for the FAS, the mITT Population, the mITT On-Treatment Population, the PP Population, and the Safety Population. Demographic characteristics data will be provided in participant listings.

3.3.5 Medical History

Medical history will be coded to system organ class and preferred term using the current Medical Dictionary for Regulatory Activities (MedDRA) version. Counts and percentages of subjects with medical history by system organ class (SOC) and preferred term (PT) will be summarized by treatment group and in total based on all randomized subjects.

A listing of all medical history data will be provided.

3.3.6 Concomitant Medications

The Prior & Concomitant Medications case report form where medication start and stop dates are recorded, will be used to determine whether the medications are prior or concomitant to the study treatment. Concomitant medications are defined as those used on or after the first dose of the study drug. Prior medications are defined as those used prior to and stopped before the first dose of study drug. All prior and concomitant medications will be coded using the current World Health Organization (WHO) Drug Dictionary. Counts and percentages of subjects taking prior and concomitant medications will be summarized by anatomical therapeutic chemical (ATC) class and preferred term by treatment group and overall, for the Safety Population.

Concomitant medications will be listed.

3.3.7 Study Drug Exposure and Compliance

Participant' exposure to randomized study drug will be summarized with descriptive statistics for the Safety Population and mITT On-Treatment Population. Days of exposure to study drug will be calculated as

date of last dose of study drug - date of first dose of study drug + 1,

For participants whose date of first dose from the initial kit dispensed was not available, the date of randomization will be used to assign the date of first dose. For subjects who failed to provide the date of last dose of study drug, the earliest date between the end of treatment date and the date of the end of study/early termination will be used.

Days of exposure to study drug will be summarized by treatment group based on the Safety Population with counts and percentages of subjects with exposure in the following categories:

- <3 weeks
- 3 <5 weeks
- 5 < 7 weeks
- 7 <9 weeks
- 9 <11 weeks
- >=11 weeks

Summary statistics will be presented for overall compliance to study drug by treatment group and in total. Counts and percentages of participants will also be tabulated by groups with overall compliance <80%, 80% to 120%, and >120%.

The percentage overall compliance to obicetrapib tablets will be calculated as:

$$\frac{actual\ tablets\ taken}{expected\ study\ drug\ taken} \times 100$$

The percentage overall compliance to ezetimibe capsules will be calculated as:

$$\frac{actual\ capsules\ taken}{expected\ study\ drug\ taken} \times 100$$

The percentage overall compliance to FDC tablet will be calculated as:

$$\frac{\textit{actual tablet taken}}{\textit{expected study drug taken}} \times 100$$

The percentage overall compliance to study drug will be calculated as:

$$\frac{\textit{actual study drug taken}}{\textit{expected study drug taken} * 3} \times 100$$

The expected study drug taken will be calculated as the earliest date between the end of treatment date and the date of early termination – the date of randomization- missed doses +1 (missed

doses defined as number of doses missed during IP interruptions due to AE or IP interruptions that are longer than 14 days).

The actual study drug taken is reported on the electronic case report form (eCRF). If no kits are returned, it will be assumed that all study drug from that kit were used.

Study drug interruptions due to AE or IP interruptions longer than 14 days will be listed.

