5.5.2 Study Drug Preparation and Dispensing

At Visit 2 (Day 1), participants will receive 1 kit (containing 36 FDC tablets or matching placebo tablets, 36 obicetrapib tablets or matching placebo tablets, and 36 ezetimibe capsules or matching placebo capsules totaling 108 tablets/capsules per kit) with the study drugs appropriate for the participant's treatment group. At Visit 3 (Day 28), participants will receive 2 kits as described above. The 2 kits provide sufficient supplies for 56 days of dosing, with enough for an extra 16 days of dosing in case the participant needs to postpone Visit 4 (Day 84). Each individual kit will provide a sufficient supply for 28 days of dosing, with enough for an extra 8 days of dosing. Participants will be instructed to take 3 units from the kit each day. The kit will be clearly labelled to indicate which tablets and capsule to use on each day. Participants will be instructed to bring all unused study drugs to the site at the next visit.

This study protocol includes contingency measures to manage disruptions due to COVID-19 control measures, including modifications to dispensation of the study drugs specific to situations where COVID-19 is impacting study conduct. See Section 3.1.4 for details of COVID-19 contingency measures. In the absence of a COVID-19 impact, it is expected that Investigators and participants follow the protocol requirements as set forth.

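### SAP 3.3.7 biases the descriptive compliance table upward: unreturned supply counts as fully taken, and recorded interruptions longer than 14 days leave the denominator whatever their cause

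*SAP*

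**What the plan says.** SAP 3.3.7 defines overall compliance as units actually taken divided by three times the expected days, with a similar ratio for each of the three products. It is one figure over the whole treatment period; no per-kit or per-visit figure is defined. Results are summarized by arm and counted in three bands: below 80%, 80% to 120%, and above 120%.

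- **Numerator.** Units taken come from the eCRF. For supply that does not come back: "If no kits are returned, it will be assumed that all study drug from that kit were used".
- **Denominator.** "The expected study drug taken will be calculated as the earliest date between the end of treatment date and the date of early termination", less the randomization date and less missed doses, plus one. What is subtracted is missed "doses defined as number of doses missed during IP interruptions due to AE or IP interruptions that are longer than 14 days". An interruption due to an adverse event (AE) is therefore removed at any length, and any other interruption is removed once it exceeds 14 days. The same section says that these interruptions will be listed.
- **Supply.** Protocol 5.5.2 dispenses one kit on Day 1. After that, "At Visit 3 (Day 28), participants will receive 2 kits as described above". On kit size: "Each individual kit will provide a sufficient supply for 28 days of dosing, with enough for an extra 8 days of dosing", and "totaling 108 tablets/capsules per kit".

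Protocol 5.5.4 describes compliance as a count of unused units and mentions neither rule.

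**The concern.** Both rules replace missing or unfavourable information with a favourable value. An unreturned kit says nothing about how much was taken, yet it is credited with its full contents, including the 8-day reserve. A long interruption without an AE is a plain form of not taking the drug, yet beyond 14 days it costs nothing, while a shorter one does.

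At stake is whether the by-arm compliance table, with its fixed bands, describes adherence. This matters most for placebo. The mITT On-Treatment Population (SAP 3.2.4) applies an obicetrapib concentration threshold only in the two obicetrapib-containing arms, and no drug concentration can confirm that placebo was taken. Placebo is the comparator in two of the four co-primary comparisons.

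**Working it through.** **Inputs.** Protocol 5.5.2: 36 of each of three units per kit, one kit on Day 1 and two on Day 28. On daily use: "Participants will be instructed to take 3 units from the kit each day". Protocol 3.1.2: Visits 3 and 4 have windows of ±7 days. Protocol 5.5.3: the dose on a visit day comes from the earlier kit. SAP 3.3.7: the formula and both rules.

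**The plan's own figures.** The documents give no compliance percentage for these cases, so only the kit contents can be reproduced: 28 + 8 = 36 days; 3 × 36 = 108 units per kit; 2 × 36 = 72 = 56 + 16 days. All agree. Below I count daily doses, so the factor of 3 cancels. Three kits hold 3 × 36 = 108 daily doses.

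**Rule 1: can the credited doses have been taken?** Within the visit windows, once daily:

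- Day 1 kit: with Visit 3 as late as Day 35, at most 35 doses, against 36 credited.
- Both Day 28 kits: with Visit 3 on Day 21 and Visit 4 on Day 91, Days 22 to 91 give at most 70, against 72 credited.
- All three kits: at most 91, against 108 credited.

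One of the two Day 28 kits could be emptied if the other was used less. A kit cannot yield more than it holds, so the credited number is never too low.

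**Rule 1: scores.** Compliance = credited doses / expected days.

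| Case | Score under the SAP | True use |
|---|---|---|
| No kit returned, treatment ends Day 84 | 108/84 = 128.6% | unknown |
| Same, ends Day 77 | 108/77 = 140.3% | unknown |
| Same, ends Day 91 | 108/91 = 118.7% | unknown |
| Day 1 kit lost, 56 doses from the others | (36 + 56)/84 = 109.5% | at least 56/84 = 66.7% |
| Day 1 kit lost, 70% adherence throughout | (36 + 0.7 × 56)/84 = 75.2/84 = 89.5% | 70% |
| Both Day 28 kits lost, 28 doses from the Day 1 kit | (28 + 72)/84 = 119.0% | at least 28/84 = 33.3% |
| Treatment ends Day 10, Day 1 kit kept | 36/10 = 360% | unknown |

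The three rows with some kits lost and others returned assume that the rule works kit by kit. The other rows hold on either reading, because nothing dispensed was returned. Losing one Day 28 kit also gives 92/84 = 109.5% if 28 doses came from each kit that was returned. The last row takes Day 10 as the end of treatment date.

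**Rule 2.** Let g be the length in days of a recorded interruption without an AE, with otherwise perfect dosing, all supply returned, and treatment ending on Day 84. The score is (84 − g)/84 for g ≤ 14 and (84 − g)/(84 − g) for g > 14.

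| g | Score under the SAP | If kept in the denominator |
|---|---|---|
| 14 | 70/84 = 83.3% | 83.3% |
| 15 | 69/69 = 100% | 69/84 = 82.1% |
| 17 | 67/67 = 100% | 67/84 = 79.8% |
| 21 | 63/63 = 100% | 63/84 = 75.0% |
| 42 | 42/42 = 100% | 42/84 = 50.0% |

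The score jumps from 83.3% to 100% when one more day is missed. From 17 days on, the rule also moves the participant from the lowest band to the middle one.

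**The case against.** The strongest reply is that this is one descriptive table, and much of that stands. Days of exposure come from first and last dose dates and use neither rule. The primary analysis is ITT under a treatment policy strategy. The Per-Protocol Population rests on major protocol deviations, and the On-Treatment population on Day 84 obicetrapib concentration. The subtracted interruptions are listed. Participants are told to bring back unused drug, and the documents do not suggest that many kits go missing.

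Two stronger readings are tempting, and the documents do not support them.

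- A reader might infer that any unreturned kit scores 129%. The ratio 36/28 has that value, but the SAP has no per-kit compliance. A single lost kit moves the overall figure to about 109.5%. The 128.6% needs all three kits missing and treatment ending on Day 84, and it lands in the band above 120%, where it looks like over-compliance, not full compliance.
- A reader might infer that any unexplained gap is forgiven. Only recorded interruptions are subtracted. A gap that is not recorded as one, and scattered missed doses, still lower the score through the count of returned units.

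Two further points stand in part. The reserve exists to cover postponed visits, so for the Day 1 kit the excess over what is possible can be as small as one dose; it does not vanish within the window. And limiting compliance to periods when drug was meant to be taken is a legitimate definition. That can justify removing supply-driven gaps, but not a cut-off on length alone, for which the SAP gives no reason.

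**Conclusion.** The concern holds for the compliance table and no further. Unreturned supply gives 128.6% if nothing comes back by Day 84 (118.7% to 140.3% across the final visit window). If the rule is applied kit by kit, one or two lost kits can place a participant in the 80% to 120% band when true use is 70% or as low as 33.3%. A recorded interruption without an AE scores better at 15 or 42 days (100%) than at 14 days (83.3%).

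These figures assume once-daily dosing, treatment ending on Day 84 unless stated, and the kit contents in Protocol 5.5.2. How many participants would be affected cannot be derived from the documents.

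A reader might go on to infer that efficacy results or an analysis population are distorted. The documents do not support that: none of the populations or efficacy analyses they define uses the compliance percentage. Whether the separate Protocol Deviation Plan uses it to identify Per-Protocol exclusions cannot be seen here. The correction is worth making because the table is planned by arm, the error is never downward, and the change is small.

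**What to change.** Amend SAP 3.3.7 before unblinding.

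1. **Unreturned supply.** State that the rule works by dispensing interval: the Day 1 kit, and the two Day 28 kits together, because they share one interval. If supply for an interval is not returned, set that participant's overall compliance to missing and show it in a separate unknown category with counts by arm. Optionally give bounds, taking doses in that interval as anything from 0 to the number of days in it. For both Day 28 kits lost, with 28 doses from the Day 1 kit, the bounds are 28/84 = 33.3% and (28 + 56)/84 = 100%. Dropping the interval from numerator and denominator is not enough: this participant would then score 28/28 = 100%.
2. **Interruptions.** Drop the 14-day criterion. Subtract only doses missed in interruptions due to an AE or a documented site or supply cause, such as the COVID-19 dispensing disruption foreseen in the protocol. Count doses missed in any other interruption as not taken, whatever its length, and align the listing with this.

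**Cost.** A few SAP sentences and an extra table category. Some participants will have missing compliance, and the cause of each interruption must be available in the data. No efficacy analysis in these documents changes.
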